10.1 Schedule of Events

Follow-up protocol required evaluations should be performed at the trial site, however remote visits via phone contact are permitted, if an in-person clinic visit is not feasible. Every effort should be made to obtain the follow-up transthoracic echocardiogram (TTE), when required, following a phone contact. The protocol required evaluations for each trial interval are listed as follows and summarized in **Table 4**.

In general, the examinations and procedures in this trial are standard of care. At certain sites, some examinations and procedures during identified follow-up such as TTE image acquisition, Quality of Life Questionnaires (EQ-5D and KCCQ), Modified Rankin Score, 6-Minute Walk Test, 12-Lead ECG and Stress

Version 4.0, 15-Dec-2021

Page 32 of 131

Echocardiogram (at select sites) are not standard-of-care. All local and national regulations will be adhered to with regard to EC/IRB/REB and regulatory authority submissions, as applicable.

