7.2 General Methodology

Descriptive statistics of continuous outcomes will be presented by treatment arm and include count, mean, median, standard deviation, first and third quartiles, minimum and maximum. For categorical outcomes, the number and percentage of subjects in each category will be presented by treatment arm.

For time-to-event outcomes using Kaplan-Meier methods, the time points of 30 days, 1 year, 2 years, 3 years, 4 years, and 5 years will correspond to 30, 365, 730, 1095, 1460, and 1825 days post-implant, respectively. For each applicable time point, the event or event-free rate, the number of subjects at risk, the number of subjects with an event, the Greenwood standard error of the estimate, and the log-log transformed 95% confidence interval using the Greenwood standard error will be reported. For subjects with an event, the date of event will be based on the first event occurrence. For subjects without an event, date of censoring will be based on the latest of all follow-up visits, assessments, and events (for non-death events). Methods which account for interval censoring may be considered for survival analysis of events based on echo assessment.

For analyses using echocardiographic data, only echo data corresponding to the implanted study valve will be used; data post-explant or after reintervention will be excluded from analysis.

SMART Trial Statistical Analysis Plan Form Revision 5.0 Page 14 of 27 Mectronic

Subject data listings and tabular and graphical presentations of results will be provided. Unless otherwise specified, a two-sided 0.05 level of significance will be used to declare treatment arms significantly different.

All statistical analyses will be performed using SAS version 9.4 or higher (SAS Institute, Cary, North Carolina, USA) or other widely accepted statistical or graphical software.

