7.4 Handling of Missing, Unused, and Spurious Data and Dropouts

Every effort will be undertaken to minimize missing data. In time-to-event outcomes, dropouts will be censored at the time of discontinuation, consistent with the Kaplan-Meier approach. Unless otherwise specified, no statistical techniques will be used to impute missing data. The number of subjects included in each analysis will be reported so that the reader can assess the potential impact of missing data. To evaluate the potential impact of missing data on study results, sensitivity analyses will be performed for the primary endpoints which will include a tipping point analysis.

In the case of partial dates, if only the month and year are known, the event or assessment will be analyzed as if it occurred on the 15th of that month. If only the year is known, the event or assessment will be analyzed as if it occurred on June 30th of that year. Imputation of partial dates is subject to the restriction that pre-implant events must occur between the date of informed consent and the date of implant and post-implant events must occur after the date of implant and prior to date of study exit.

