- Valve-related dysfunction (mean aortic valve gradient \geq 20 mmHg, EOA \leq 0.9-1.1 cm² and/or DVI <0.35m/s, AND/OR moderate or severe prosthetic valve regurgitation)

Page 23 of 27

Note that the EOA threshold of 0.9 applies for subjects with BSA <1.6 m² and EOA threshold of 1.1 applies for subjects with BSA \geq 1.6 m². The endpoint will be evaluated at each time point using the point estimates from a Kaplan-Meier analysis. Components of the endpoint will be reported on the echo core lab CRF, the follow-up visit CRF, and the CEC CRF. Events occurring within 12 months and annually to 5 years, will be counted towards the event rate at each time point. Time to event for the overall composite will be based on the earliest component event; components of the event (NYHA class, valve-related dysfunction) that are detected on scheduled follow-up visits (e.g., 12 months) will be the minimum of the assessment date or the visit target date (e.g., 365 days). Censoring time will be the last available time where subjects are known to be fully event free. Subjects with an event within 30 days will be excluded from the analysis. Analysis of the endpoint will use the Implanted analysis set.

5. Components of the primary clinical endpoint at 12 months and annually to 5 years:

- Mortality •
- **Disabling stroke** •
- Heart failure rehospitalization

Mortality, disabling stroke, and heart failure rehospitalization will be adjudicated by the CEC and analysis will be based on data collected on the CEC adjudication form. Each component will be analyzed with Kaplan-Meier survival analysis according to Section 7.2 for each time point. Analysis of the endpoint will use the AT analysis set.

6. New pacemaker implantation rate at 30 days, 12 months and annually to 5 years

New pacemaker implantation will be reported according to data reported by the investigator on the Permanent Pacemaker Implant CRF. The endpoint will be analyzed with Kaplan-Meier survival analysis according to Section 7.2 for each time point. Analysis of the endpoint will use the AT analysis set, excluding patients with PPI or ICD prior to the study TAVR procedure.

7. Aortic valve re-intervention at 30 days, 12 months and annually to 5 years

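### Clinical efficacy (SAP 7.9.4 #4): censoring at the last fully event-free time makes the Kaplan-Meier rate read too high to the extent that complete NYHA/echo visits are missing or fall before the target date

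*SAP*

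**What the plan says.** SAP 7.9.4 #4 combines events dated when they happen (death, stroke, hospitalisation for valve-related symptoms or heart failure) with states seen only when assessed (NYHA class III or IV, and echo-based valve dysfunction). Subjects with an event within 30 days are excluded. Four rules govern the estimate:

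- Estimator: "The endpoint will be evaluated at each time point using the point estimates from a Kaplan-Meier analysis".
- Event time: "Time to event for the overall composite will be based on the earliest component event". Findings at scheduled visits are dated at the assessment or the visit target day, whichever is earlier.
- Counting: "Events occurring within 12 months and annually to 5 years, will be counted towards the event rate at each time point". Nothing limits hard events to the period before the last complete visit.
- Censoring: "Censoring time will be the last available time where subjects are known to be fully event free".

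The last rule departs from the SAP's general rules. Section 7.2 censors at the latest follow-up of any kind, and under Section 7.4 "dropouts will be censored at the time of discontinuation, consistent with the Kaplan-Meier approach". Section 7.2 permits methods for interval-censored echo events but does not require them. A supportive analysis of that type is named for #10 (bioprosthetic valve dysfunction, years 2 to 5), and none for #4.

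**The concern.** The phrase in #4 does not mention a complete visit, but no other reading is practical: freedom from all components can be established only where NYHA and echo are both evaluable. Hard events need no such visit. Protocol 10.1 adds that "remote visits via phone contact are permitted, if an in-person clinic visit is not feasible", so a subject's vital status and hospitalisations can be known while the echo is absent.

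Take two subjects, both clean at a 30-day visit on day 37, neither with an evaluable 12-month echo. One dies on day 300: that subject is at risk from day 37 to day 300 and counts as an event. The other is reached by phone on day 365 and has had no stroke or hospitalisation: that subject is censored on day 37. How long each stays at risk is decided by the outcome. Kaplan-Meier does not allow this, and the bias arises even when the reason for the missing echo has nothing to do with prognosis. At stake are the composite rates reported by arm each year to 5 years.

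**Working it through.** **Inputs.** The plan states no rate, power or completeness figure for #4, so there is nothing of its own to reproduce. The 16% used below is the planning rate for a different composite (SAP Section 6) and serves only as an anchor. All other rates are assumptions.

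**Closed form at 12 months.** Let C be the proportion with a hard event between day 30 and day 365, and m the share of the remaining subjects with no complete 12-month visit. Under #4 that share is censored near day 30, before nearly all hard events. The effective denominator is C + (1−C)(1−m) = 1 − m(1−C), so the hard-event part reads C / [1 − m(1−C)] instead of C.

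With C = 0.16 and m = 0.10: 0.16 / (1 − 0.084) = 0.16 / 0.916 = 17.47%, an error of +1.47 points. Let a proportion v = 0.15 of assessed subjects have a visit-found event. The true composite is 1 − 0.84 × 0.85 = 28.60%. Under #4 it is 1 − (1 − 0.1747) × 0.85 = 29.85%, an error of +1.25.

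Error on the composite (points, v = 0.15):

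| C | m = 5% | m = 10% | m = 15% |
|---|---|---|---|
| 8% | +0.33 | +0.69 | +1.09 |
| 12% | +0.47 | +0.98 | +1.55 |
| 16% | +0.60 | +1.25 | +1.96 |

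**Two other rules, same inputs (C = 0.16, m = 0.10, v = 0.15).**
- Section 7.2 rule: subjects without a 12-month echo stay in the denominator on day 365 but cannot show a finding. The visit factor becomes 1 − 0.90 × 0.15 = 0.865, and the composite 1 − 0.84 × 0.865 = 27.34%, which is 1.26 points too low.
- Symmetric rule: these subjects leave just before the day-365 findings are counted. The visit factor is 0.85 and the composite 28.60%, which is correct.

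**Simulation to year 5.** 200,000 subjects per scenario, starting at day 30, with data cut after each annual visit. Hard events were 10% or 16% in year 1 and 7% or 10% per year later. Visit-found events were 10% to 15% at 12 months and 4% to 5% per year later. Missingness was unrelated to outcome unless stated. Errors of the #4 rule in points:

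| Scenario | Year 1 | Year 5 |
|---|---|---|
| All visits complete, on or after target | 0.0 | 0.0 |
| Intermittent, 5% of visits incomplete | +0.4 to +0.5 | +0.2 |
| Intermittent, 10% | +0.7 to +1.1 | +0.4 |
| Intermittent, 20% | +1.7 to +2.5 | +1.1 |
| Cumulative loss, 6% by year 1 and 17% by year 5 | +0.4 to +0.6 | about +2.0 |
| Cumulative loss, 10% and 26% | +0.7 to +1.1 | about +3.6 |
| Cumulative loss, 19% and 47% | +1.6 to +2.3 | about +7.5 |
| Cumulative loss, concentrated in frailer subjects | +0.5 to +0.9 | +2.2 to +4.6 |
| Nothing missing, visits spread over the protocol windows | 0.0 | +1.5 to +1.6 |

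Intermittent gaps do not build up, because a later complete visit restores the subject's time. The last row reflects Protocol 10.3, where the 12-month window opens at the target day but later windows are ±30 or ±60 days. Event-free subjects seen early are censored before the target date, while findings at late visits are moved back onto it. At year 2 this alone gives +2.1 to +2.3. Windows and cumulative loss together give +3.5 to +9.4 at year 5.

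In the same simulations with non-informative missingness, the Section 7.2 rule read low by 0.5 to 2.6 points at year 1 and 0.1 to 4.9 at year 5. The symmetric rule stayed within 0.2 point at every year.

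**Between arms.** With equal completeness and assumed true 12-month rates of 22.4% and 33.8% (difference 11.4), the rates at 10%, 20% and 30% incomplete are 23.4/34.7, 24.6/35.8 and 26.0/37.0, so the differences are 11.3, 11.2 and 11.0. With unequal completeness, take two arms with the same true rate (C = 16%, v = 15%) and 5% against 15% incomplete. The table gives +0.60 against +1.96, a spurious difference of 1.36 points.

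**The case against.** The strongest reply is that little depends on this endpoint. SAP 7.9.4 makes it descriptive, with no hypothesis test. Mortality, disabling stroke and heart-failure rehospitalisation appear separately under #5 with the ordinary censoring rule, echo measures under #11, and adjudicated events under Section 7.10. That stands, and it limits the consequence.

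The protocol also works against missing echoes. Section 10.1 asks sites to try to obtain the echo after a phone contact, and Section 10.3 keeps out-of-window visits in the analysis and prefers a late visit to a missed one. That stands too: it limits the size, though by how much cannot be read from the documents.

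The present rule also avoids the opposite error. The Section 7.2 rule treats subjects as free of valve dysfunction at times when nobody looked, and reads low. This explains the choice but does not make the result unbiased.

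The reply that Section 7.2 already allows interval-censoring methods does not settle the matter, because the option is discretionary and the only such analysis named in 7.9.4 belongs to #10.

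A reader might go further and infer that every event-free subject loses time, or that the error must grow each year to year 5. The documents do not support either. A subject whose last due visit is complete and on or after target loses nothing, and growth requires cumulative loss of complete visits, for which the plan gives no figure.

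**Conclusion.** The point holds in conditional form. As written, #4 makes censoring depend on outcome, and the rate at each annual analysis is biased upward whenever complete visits are missing or precede the target date. The ranges of +0.4 to +2.5 points at year 1 and about +2 to +8 points at year 5 rest on assumed event rates, assumed completeness and non-informative missingness; the year-5 range also needs accumulating loss.

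The upward direction applies to the time point current at each data cut. If year 1 is re-estimated later from 5-year data, it can fall below the truth: in one scenario with 20% intermittent missingness, 20.4% against a true 22.6%. Subsequent hard events then decide who was still at risk on day 365.

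A reader might also infer that the comparison of the two valves is undermined. With equal completeness the 12-month difference hardly moves; distortion arises mainly if completeness differs by arm, which is why the counts should be shown. No success criterion of the trial depends on #4.

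**What to change.** Replace the censoring sentence in SAP 7.9.4 #4 with a rule that ignores what happens later:

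- Every subject leaves the risk set at the target date of the first scheduled visit without a complete NYHA and echo assessment, or at end of follow-up if earlier, whether or not a hard event follows.
- Complete in-window visits are assigned to the target date, for events and for censoring alike.
- State the order on tied days. Subjects with an incomplete visit leave just before the findings dated on that day; subjects with a complete clean visit are still counted. If the tie is left to the usual Kaplan-Meier convention, the incomplete subjects stay in the denominator and the 1.26-point understatement shown for the Section 7.2 rule returns.
- Report the number of complete visits by arm at each time point.

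Do not simply go back to the Section 7.2 rule. Component-specific risk sets are an acceptable alternative: all subjects under follow-up for hard events, and only assessed subjects for NYHA and valve dysfunction. They keep more hard events but need bespoke intervals, and they read 0.4 to 1.1 points high at year 5 when an undetected valve or NYHA state doubles the hard-event hazard.

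Cost: SAP wording and modest programming, with no new data. Hard events after a first incomplete visit no longer enter this composite, although mortality, disabling stroke and heart-failure rehospitalisation remain visible under #5. The correction still assumes that missing visits are non-informative.

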10.1.5 Follow-Up Evaluations

All treated subjects will undergo follow-up evaluations at the following time points post procedure. See section 10.3 for appropriate visit windows.

30 days (between 30 – 45 days post procedure)

- Clinical Assessment including physical examination
- Use of relevant medications including anticoagulants and antiplatelets
- NYHA Classification
- TTE
- 6-minute Walk Test (refer to Appendix Section 18.1)
- Quality of Life Questionnaires- EQ-5D and KCCQ
- 12-Lead ECG
- Adverse Event Review

12 Months (Day 365 + 30 days)

- Clinical Assessment including physical examination
- Use of relevant medications including anticoagulants and antiplatelets
- NYHA Classification
- TTE
- 6-minute Walk Test (refer to Appendix Section 18.1)
- Quality of Life Questionnaires- EQ-5D and KCCQ
- 12-Lead ECG
- Adverse Event Review
- Stress echocardiogram- (conducted at select sites. A CIP addendum detailing the assessment will be provided separately)

2 Years (Implant anniversary date and ± 30 days)

- Clinical Assessment including physical examination
- Use of relevant medications including anticoagulants and antiplatelets
- NYHA Classification
- TTE
- 6-Minute Walk test (refer to Appendix Section 18.1)
- Quality of Life Questionnaires- EQ-5D and KCCQ
- Adverse Event Review

Annual 3-5 years (Implant anniversary date and ± 60 days)

- Clinical Assessment including physical examination
- Use of relevant medications including anticoagulants and antiplatelets

SMART Trial Clinical Investigation Plan	Form
Version 4.0, 15-Dec-2021 Page 38 of 131	Medtronic

- NYHA Classification
- TTE
- 6-Minute Walk test (refer to Appendix Section 18.1)
- Quality of Life Questionnaires- EQ-5D and KCCQ
- Adverse Event Review

Other Evaluations

- In addition to an assessment at baseline, a Modified Rankin Score assessment should be conducted at 30 and 90 days after onset of any confirmed or suspected neurological event.
- In addition to laboratory tests at baseline, laboratory test results relevant for event adjudication (i.e., hemoglobin to adjudicate bleeding events) should be collected

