For subjects that experience more than one component of the composite, the earliest event time will be used for the analysis. For subjects that do not experience any component of the composite within the timeframes described above, the censoring time will be the time of the latest echo known to be free of HSVD and NSVD (requires all evaluable data for all three of: effective orifice area, mean gradient, and aortic regurgitation).

The endpoint will be presented with the Kaplan-Meier estimate of the composite event rate at 365 days (cumulative incidence) within treatment arms along with corresponding Greenwood Standard error, the estimated difference in event rates (SE TAV - BE TAV) at 365 days with corresponding upper limit from the two-sided 95% large sample confidence interval, and the one-sided p-value for the superiority

Revision 5.0

Page 18 of 27

hypothesis. The two-sided confidence interval and test statistic will be calculated as described for the clinical outcome composite endpoint as

$$(1 - \hat{S}_{MDT}) - (1 - \hat{S}_{EW}) \pm z_{\alpha/2} \sqrt{\hat{V}(\hat{S}_{MDT}) + \hat{V}(\hat{S}_{EW})},$$

where \hat{S}_{MDT} and \hat{S}_{EW} are the survival point estimates at 365 days from the Kaplan-Meier analysis for the Medtronic SE TAV and Edwards BE TAV, respectively, and $\hat{V}(\hat{S}_{MDT})$ and $\hat{V}(\hat{S}_{EW})$ are the Greenwood variance estimates corresponding to each survival point estimate. The test statistic will be calculated as

$$z = \frac{(1 - \hat{S}_{MDT}) - (1 - \hat{S}_{EW})}{\sqrt{\hat{V}(\hat{S}_{MDT}) + \hat{V}(\hat{S}_{EW})}}$$

If the one-sided p-value is less than or equal to 0.025, the endpoint will be considered met. The components of BVD will be summarized descriptively. The analysis will be performed using the Implanted analysis set.

The following additional supportive analysis for the primary endpoint will be performed using the implanted population:

- Repeat analysis using Kaplan-Meier approach described above, excluding "late" 12-month echos (after end of 12-month visit window: 395 days).
- A tipping point analysis using the Kaplan-Meier estimate at 365 days that will systematically consider each subject with missing outcome at Day 365 as an event or a non-event at 365-days in all combinations.

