The endpoint will be derived following the same principles as described for the valve function composite co-primary endpoint in **Section 7.9.2**, with same method used for the primary analysis at 12 months. Cutoff days for point estimates are 730, 1095, 1465, and 1825 for analysis time points of 2 years, 3 years, 4 years, and 5 years, respectively. Time to event for events detected on scheduled follow-up echos at 2 years, 3 years, 4 years, and 5 years will be the minimum of the echo date or the visit target date (e.g., 365 days). As in the primary endpoint analysis, HSVD and NSVD events detected through the maximum of the annual visit echo date or the end of the corresponding visit window will be counted to ensure inclusion of events detected on unscheduled echos. Thrombosis, endocarditis, and aortic valve re-intervention events detected through the visit target date (730, 1095, 1465, and 1825 days respectively) will be counted. Components of the endpoint will also be reported at each time point. Analysis will use the Implanted analysis set.

Given the increasing impact of mortality on availability of the BVD endpoint at later time points, a survival analysis for interval-censored outcome data in the presence of competing risks will be performed as a supportive analysis, as described in the list of supportive analyses at the end of **Section 7.9.2**.

11. Echocardiographic measurements (i.e., EOA, mean gradient, PVL, LV mass regression, and DVI (severe <0.25, moderate 0.25-0.5, mild >0.5)) at discharge, 30 days, 12 months and annually to 5 years

Echocardiographic measurements will be summarized descriptively based on core lab reported data at each time point within arm. Analysis will be performed using the Implanted analysis set.

EOA and mean gradient will be analyzed as continuous data. Change from baseline in EOA and mean gradient will be summarized descriptively within each arm. Paravalvular leak (PVL) and DVI (severe <0.25, moderate 0.25-0.5, mild >0.5) will be analyzed descriptively as categorical data.

12. Mean gradient ≥ 20 mmHg based on stress echocardiogram at 12 months at select sites

Mean gradient \ge 20 mmHg based on stress echocardiogram at 12 months will be summarized descriptively as categorical data for each treatment arm. Stress echocardiogram will only be

SMART Trial Statistical Analysis Plan	Form
Revision 5.0 Page 25 of 27	Medtronic

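### When some visits fall before the target day, the 5-year Kaplan-Meier rates for BVD and clinical efficacy read slightly too high, because late-found events are moved back to the target day but clean early visits are not moved forward

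*SAP*

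**What the plan says.** **BVD at years 2 to 5 (SAP 7.9.4 #10).** The time of an event found at a scheduled echo "will be the minimum of the echo date or the visit target date (e.g., 365 days"). HSVD and NSVD are counted up to the later of the visit echo and the window end. Otherwise the endpoint follows SAP 7.9.2, where for event-free subjects "the censoring time will be the time of the latest echo known to be free of HSVD and NSVD".

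**Clinical efficacy (SAP 7.9.4 #4).** For NYHA class and valve-related dysfunction, the event time "will be the minimum of the assessment date or the visit target date (e.g., 365 days"). For the rest: "Censoring time will be the last available time where subjects are known to be fully event free".

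**Windows (Protocol 10.1.5 and Table 5).** The first annual window has no early side: "12 Months (Day 365 + 30 days"). The later ones do: "2 Years (Implant anniversary date and ± 30 days") and "Annual 3-5 years (Implant anniversary date and ± 60 days"). They open on days 700, 1035, 1400 and 1765. Protocol 10.3 also analyses visits made outside the window. Year 5 is the last scheduled visit.

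**Related handling.** #10 plans an interval-censored competing-risk analysis of BVD as supportive. SAP 7.2 says: "Methods which account for interval censoring may be considered for survival analysis of events based on echo assessment". It also has the number at risk reported at each Kaplan-Meier time point. SAP 7.9.4 makes all these endpoints descriptive.

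**Year-4 day.** #10 uses 1465 twice. SAP 7.2 and Protocol Table 5 use 1460.

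**The concern.** The two outcomes of one visit are dated by different rules. Take a subject whose year-5 echo is clean on day 1780. That subject is censored on day 1780. Another subject, seen on day 1860 with BVD, has the event placed on day 1825. On day 1825 the first subject is no longer in the risk set, although the visit was attended and the result is known. The late-found events are therefore divided by too few subjects, and the Kaplan-Meier step on the target day is too large.

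At years 2 to 4 a later clean visit puts the early attendee back in the risk set, so the effect largely disappears once later data exist. At year 5 no later visit follows. Long-term valve function through 5 years is the trial's stated secondary objective (SAP 4.2), so the affected number is one that will be reported prominently.

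**Working it through.** The plan states no expected rate for these late endpoints, so there is no figure to reproduce. The starting rates used here, 14% (SE) and 36% (BE) at 12 months, are the plan's BVD assumptions (SAP 6). They do return its 60 per arm (one-sided 0.025, 80% power).

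**Inputs not in the documents, assumed.** e = share of year-5 visits before the target day; q = yearly onset of new BVD after year 1, taken as the share newly found at each annual visit.

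**Formula.** As clean early attendees leave one by one, early-found events add about -q·ln(1-e) to the cumulative hazard, which is a survival factor of (1-e)^q. On the target day only late attendees remain, and a fraction q of them have events, a further factor (1-q). With p the true cumulative rate:

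- reported rate = 1 - (1-p)(1-e)^q
- excess = (1-p)[1 - (1-e)^q]
- 1-p = 0.86(1-q)^4 for SE and 0.64(1-q)^4 for BE

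Small illustration: 100 subjects at risk, 50 seen early and 50 late, with 2 new events in each half. The true figure is 4%. The estimate is 1 - 0.5^0.04 × 0.96 = 1 - 0.973 × 0.96 = 6.6%.

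**5-year excess for BVD.** Example, q = 5%, e = 50%: 1 - 0.5^0.05 = 0.0341; SE 0.86 × 0.8145 × 0.0341 = 2.4 points; BE 0.64 × 0.8145 × 0.0341 = 1.8 points.

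| Onset per year | e = 0 | e = 10% | e = 25% | e = 50% |
|---|---|---|---|---|
| 2%, SE / BE | 0 / 0 | 0.2 / 0.1 | 0.5 / 0.3 | 1.1 / 0.8 |
| 5%, SE / BE | 0 / 0 | 0.4 / 0.3 | 1.0 / 0.7 | 2.4 / 1.8 |

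**Arm difference (BE minus SE), e = 50%.**

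| Onset SE / BE | True | Reported |
|---|---|---|
| 2% / 2% | 20.3 | 20.0 |
| 5% / 5% | 17.9 | 17.3 |
| 2% / 5% | 27.2 | 27.9 |

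With SE 1% and BE 5% the excesses are 0.57 and 1.78, so the difference widens by 1.2 points. At e = 80% the same pair gives 2.7. The difference narrows when onset is equal. It widens only if BE onset exceeds SE onset by about 1.36 to 1.51 times (q from 1% to 5%).

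**Simulation check** (1,000,000 subjects per arm, continuous onset, protocol windows, 5% per year). The 5-year rate under the SAP rule minus the rate when clean visits are moved forward is 0.37/0.27, 1.03/0.77 and 2.50/1.84 points (SE/BE) at e = 10%, 25% and 50%. The formula gives 0.37/0.27, 1.00/0.74 and 2.39/1.78. With e = 0 the SAP rule still reads 0.3/0.2 above truth, because late visits pick up onsets after the target day. That is a separate, small effect.

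**Clinical efficacy at 5 years** (assumed 10% visit-found at 12 months, then 3% a year, plus 8% a year death, stroke or hospitalisation). True 47.5%; reported 47.7%, 48.0% and 48.6% at e = 10%, 25% and 50%.

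**Earlier horizons.** With year-5 data in hand, a second simulation (350 per arm, 5% yearly mortality) shows a year-4 excess of about 0.3 points or less. At a 2-year data cut (5% a year, e = 50%) the excess is 2.7/2.0 points if nobody has a 3-year echo, and 1.2/0.9 if 40% do. It is lower again if the cut is later, so any 2-year figure depends on the assumed cut date.

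**Scale.** With 350 per arm and no attrition, the 95% half-width for the 5-year difference at q = 2% is 1.96 × sqrt[(0.207 × 0.793 + 0.410 × 0.590)/350] = 6.7 points; at q = 5% it is 7.1. For one arm it is about 4 to 5 points.

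**The case against.** The case for leaving this alone is fair on several counts.

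- Both endpoints are descriptive. No alpha, gatekeeping step or success rule depends on them.
- Every size above rests on assumed e and q. If sites see nobody before the target day, this bias is nil.
- For BVD, the interval-censored competing-risk analysis is firmly planned and does not rely on target days. The reported number at risk would show a thin risk set on day 1825.
- Using one convention from year 1 to year 5 keeps the curve uniform.

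The first two stand, and they set the severity and make the claim conditional. The third stands only in part: the supportive analysis and the number at risk reveal the problem but do not correct the Kaplan-Meier rate that will be quoted. For clinical efficacy, SAP 7.2 is only permissive and covers only echo-based events, so NYHA class is not reached. The fourth is weak, because the rule suits a window that opens on its target day, and the later windows do not.

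A reader might infer that the 12-month co-primary is biased in the same way. The documents do not support that: its window opens on day 365, so no in-window visit is early. A reader might also infer that the rule favours one device. That does not follow either, since the direction of the shift depends on the unknown ratio of late onset between the arms.

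**Conclusion.** The asymmetry is in the text and the direction within each arm is clear: upward, provided some visits fall before the target day. It applies to the last visit in the data, always including year 5, for BVD (#10) and the visit-found parts of clinical efficacy (#4). Under assumed e of 10% to 50% and onset of 2% to 5% a year, from 14%/36% at 12 months, the 5-year BVD excess is about 0.2 to 2.4 points for SE and 0.1 to 1.8 for BE.

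The arm difference can move either way. It moves 0.3 to 0.7 points in the three tabulated cases, but it would be wrong to take 1 point as a ceiling: with SE 1%, BE 5% and half the visits early it moves 1.2 points, and it moves more if most visits are early.

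No hypothesis test is affected and the excess is small beside sampling error, so this is a minor point. It is still worth correcting, because the rule as written biases a headline rate and the change is cheap. The year-4 cutoff is an unrelated slip and adds nothing to the severity.

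**What to change.** In SAP 7.9.4 #10 and #4, from year 2 onward, treat both outcomes of a scheduled visit alike. Keep the present dating of events. Credit an evaluable, event-free scheduled visit as event-free to the later of the visit date and the target day, capped at death or withdrawal. For #4, cap also at the last date known free of death, stroke and hospitalisation. State that completing the 5-year visit early is not withdrawal.

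An alternative is to date visit-found events at the earlier of the visit date and the window-opening day (700, 1035, 1400, 1765). It credits no unobserved time, and it also works for #4 when contact ends at an early 5-year visit, where the cap would undo the first rule. It does not correct visits made before the window opens.

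Leave the co-primary rule in SAP 7.9.2 unchanged. Separately, change 1465 to 1460 in both places in #10, to agree with SAP 7.2 and Protocol Table 5.

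**Cost.** A few SAP sentences and a small derivation change. The first rule credits up to 60 unobserved days for in-window visits; the second backdates late-found events. Neither is exact: in simulation a residual of about 0.25 points or less remained. Years 2 to 5 would follow a slightly different convention from year 1, and reported rates would be slightly lower.
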